8.3.4 Imaging (MRI/MRE) Contraindications

The imaging specialist at the site's imaging facility will be responsible for determining whether a participant is contraindicated from undergoing these procedures. In addition to the study inclusion and exclusion criteria (Sections 8.3.1 and 8.3.2), the following conditions will exclude the participant from scans:

1. History of claustrophobia, unless controlled with an anxiolytic
2. Physical limitations related to fitting into the bore of the magnet or weight greater than that allowable by the imaging instrument
3. Participants with a pacemaker, epicardial pacemaker wires, MRI-incompatible cardiac valve prostheses, MRI-incompatible vascular clips less than 2 months old, or MRI-incompatible aneurysm clips of any age
4. Participants with MRI-incompatible cochlear implants
5. Participants with spinal nerve stimulators
6. Participants with a nondetachable infusion pump
7. Participants with known metallic fragments in the body
8. Employment history that involves exposure to welding
9. Participants who have shrapnel anywhere in their body

The above list should not be used as a substitute for local clinical standards of care. The ultimate decision to perform any scan should rest with the site radiologist, the investigator, and the standard set by the IRB/EC and local institution.

If imaging is contraindicated for a participant, but the participant is otherwise eligible for the study, the participant may still participate in the study.

8.3.5 History: Medical, Surgical, Diet, and Exercise

Medical and surgical history will be collected during Screening and updated on Day 1. Medical history should be complete and comprehensive, including any history of alcohol, marijuana, and caffeine use. Surgical history should include all gastrointestinal and endocrine surgical procedures in the participant's lifetime and all other surgical procedures that occurred in the previous 5 years. Medical history will also include a fall risk assessment at Screening, and a diet and exercise history at Week 24 and Week 48/ET.

8.3.6 Dietary and Lifestyle Counseling

During Screening, after receiving the signed ICF, sites will provide all participants with the following dietary and lifestyle counseling:

- Reduce body weight (if obese or overweight) through diet and exercise
- Follow a balanced diet
- Increase physical activity
- Avoid alcohol as much as possible. However, if alcohol is consumed, do not consume ≥ 30 g/day (males) or ≥ 20 g/day (females) of alcohol during the study. This is equal to approximately 2 alcoholic drinks per day for males, and approximately 1.5 alcoholic drinks per day for females. One alcoholic drink is equal to 12 ounces (355 mL) of 5% ABV beer, 5 ounces (148 mL) of 12% ABV wine, or 1.5 ounces (44.4 mL) of 40% ABV distilled spirits

8.3.7 Concomitant Medication Restrictions

Anti-diabetic, anti-obesity, and anti-dyslipidemic medications are allowed if participants have been on stable dosing regimens for at least 3 months (12 weeks) (6 weeks for statins prior to and during the Screening Period. The investigator may contact the medical monitor regarding the stability of a participant's regimen when determining eligibility for study participation.

During study treatment, participants should refrain from using cannabinoid products.

[figure not shown]
Vitamin E is allowed; however, vitamin E doses ≥ 800 IU/day are allowed only if participants have been on stable doses for at least 6 months (26 weeks) prior to and during the Screening Period and if vitamin E treatment (≥ 800 IU/day) was not initiated after the qualifying liver biopsy was performed.

Vitamin D and calcium supplementation are permitted per local standard of care. Use of bisphosphonates, selective estrogen receptor modulators, estrogen, or teriparatide for treatment of osteoporosis is permitted if participants have been on stable doses for at least 6 months (26 weeks) prior to and during the Screening Period.

Any change in dose of these medications should be recorded in the electronic case report form (eCRF). Consult with the medical monitor if medications which could impact bone density assessments are to be added during the Double-Blind Treatment Period or during the first 6 months after the Week 52 / PTFU Visit.

Medical or surgical treatments for obesity should not be initiated while the participant is participating in the first 52 weeks of the study (i.e., from the time of informed consent until the participant completes the Week 52/PTFU Visit or discontinues participation in the study, whichever comes first).

Concomitant medications and medical and surgical treatments will not be limited after the Week 52/PTFU Visit.

8.3.8 Screen Failures and Rescreening

Screen failures are defined as participants who consent to take part in the clinical study but are not subsequently randomized. A minimal set of screen failure information is required to ensure transparent reporting of screen failure participants, to meet the Consolidated Standards of Reporting Trials (CONSORT) publishing requirements, and to respond to queries from regulatory authorities. Minimal information includes date of consent, demography, screen failure details, eligibility criteria, and any serious AEs (SAEs).

8.3.8.1 Retesting During Screening

Laboratory parameters and/or assessments that are included in the Screening procedures ([Table 1](#) in Section 1) may be repeated during the Screening Period in an effort to find all possible qualified participants. Consultation with the medical monitor may be needed to identify whether repeat testing of any particular parameter is clinically relevant.

The most current result prior to randomization is the value by which study inclusion will be assessed, as it represents the participant's most current clinical state.

8.3.8.2 Rescreening

This study will permit the rescreening of a participant who has discontinued the study as a pre-treatment failure (i.e., the participant has not been randomized/has not been treated). Consultation with the medical monitor may be needed to identify whether rescreening is clinically relevant. If rescreened, the participant must sign a new ICF.

In the event that histologic evaluation of the biopsy of an otherwise qualified participant results in a diagnosis of NASH with stage 3 fibrosis, that individual is not eligible for the present study (MB130-069) but may be considered for enrollment under protocol MB130-068 (A Phase 2b Randomized, Double-Blind, Placebo-Controlled Study Evaluating

the Safety and Efficacy of BMS-986036 (PEG-FGF21) in Adults with Nonalcoholic Steatohepatitis [NASH] and Stage 3 Liver Fibrosis). Laboratory parameters and/or assessments that were collected as Screening procedures for this study (MB130-069; [Table 1](#) in Section 1) may be utilized for the same purpose for MB130-068.

Conversely, in the event that histologic evaluation of the biopsy of an otherwise qualified participant for MB130-068 results in a diagnosis of NASH with cirrhosis, that individual is not eligible for the MB130-068 study but can be considered for enrollment under the present study (MB130-069). Laboratory parameters and/or assessments that were collected as Screening procedures for MB130-068 may be utilized for the same purpose (Table 1 in Section 1) in this study (MB130-069).

For participants who are rescreened, consult with the medical monitor to confirm which parameters and/or assessments that were collected as part of the original Screening Period procedures may be utilized.

8.3.9 Withdrawal of Participants

8.3.9.1 Discontinuation of Study Medication

Participants MUST discontinue investigational product (IP) (and non-investigational product [non-IP] at the discretion of the investigator) for any of the following reasons.

- Participant's request to stop study medication. Participants who request to discontinue study medication will be expected to complete an ET (Week 48/ET) Visit and subsequent follow-up visits/procedures per the Schedule of Activities (e.g., Week 52/PTFU; Section 1). The only exception to this is when a participant specifically withdraws consent for any further contact with him/her or persons previously authorized by participant to provide this information. Participants' withdrawal of consent should be explained in detail in the medical records by the investigator as to whether the withdrawal is from further treatment with study medication only or also from study procedures and/or Week 48/ET, Week 52/PTFU Visit, etc. (see Section [8.3.9.2](#))
- Any clinical AE, laboratory abnormality or intercurrent illness, which, in the opinion of the investigator, indicates that continued participation in the study is not in the best interest of the participant
- The participant experiences a major bone fracture or is diagnosed with osteoporosis that requires treatment
- Abnormal liver tests as defined in Section [8.5.3.1](#)
- On 2 consecutive visits (at least 2 weeks apart), a participant has an eGFR < 30 mL/min/1.73 m², according to the *Modification of Diet in Renal Disease Study* equation
- If there is a significant protocol violation. The violation should be discussed with the medical monitor prior to discontinuing study medication
- Loss of ability to freely provide consent through imprisonment or involuntary incarceration for treatment of either a psychiatric or physical (e.g., infectious disease)

illness (Note: Under specific circumstances, a participant who has been imprisoned may be permitted to continue as a participant. Strict conditions apply, and sponsor approval is required)

- The participant becomes pregnant (study medication must be discontinued immediately)
In the case of pregnancy (see Section 8.5.3.1), the investigator must immediately notify the medical monitor or designee of this event. In the event a participant becomes pregnant during a clinical study, the study medication must be discontinued immediately. In most cases, the study medication will be permanently discontinued in an appropriate manner. The medical monitor should be contacted within 24 hours of awareness of the pregnancy
- Termination of the study or program by the sponsor
- If a participant loses more than 10% of their total body weight, the investigator should contact the medical monitor. The investigator, together with the medical monitor, will then determine whether the participant should continue to take study medication

If study medication is discontinued prior to the participant's completion of the study, the reason for the discontinuation must be documented in the participant's medical records and entered on the appropriate eCRF page. The discontinuation should also be reported via the IRT. As indicated, appropriate follow-up and/or alternate medical care must be arranged for the participant. Please notify the medical monitor as soon as possible when discontinuation of study medication is being considered.

See Section 8.4.6 for details regarding dose modification and/or treatment interruption.

Participants who prematurely discontinue study medication will be expected to complete an ET Visit and subsequent follow-up visits/procedures per the Schedule of Activities, including a Week 52/PTFU Visit (Table 2 in Section 1), DXA and Immunogenicity Follow-Up Visit(s) (Table 3 in Section 1) (see Section 8.5.3.6). The only exception to this requirement is when consent is withdrawn for all study procedures or the participant loses the ability to consent freely (i.e., is imprisoned or involuntarily incarcerated for the treatment of either a psychiatric or physical illness). Participants who discontinue study medication will not be replaced (see Section 8.3.9.4).

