	Day 1 Visit	After Day 1, up to Week 24 Visits every 4 weeks (± 5 days)	Week 24 Visit (± 5 days)	After Week 24, up to Week 48 Visits every 8 weeks (± 5 days)	Week 48 Visit (± 5 days)/ Early Termination (ET)		
Weight for body mass index (BMI) calculation	X		X		X	X	See Section 8.5.1.6. The Screening value for height will be used in the BMI calculation
Waist circumference	X		X		X		See Section 8.5.1.6
Child-Pugh Turcotte scoring	X		X		X		See Section 8.5.1.7, Appendix 5
Model for End-Stage Liver Disease (MELD) scoring	X	X	X	X	X	X	All components of the MELD score should be completed on the same day. If any individual component needs to be repeated on another day, all other components must be repeated as well. See Section 8.5.1.8 and Appendix 10
Liver-related clinical outcome events	X	X	X	X	X	X	See Section 8.5.1.9
3-Level EuroQol 5 Dimension (EQ-5D-3L) quality-of-life questionnaire	X		X		X		See Section 8.5.1.10
36-Question Short Form Health Survey (SF-36) Version 2	X		X		X		See Section 8.5.1.10
Chronic Liver Disease Questionnaire-Nonalcoholic Fatty Liver Disease (CLDQ-NAFLD)	X		X		X		See Section 8.5.1.10
Clinical Safety Assessments							
Adverse events	X	X	X	X	X	X	See Section 8.5.3.1 and Appendix 9
Concomitant medications	X	X	X	X	X	X	See Section 8.3.7

Procedure/Assessment	Double-Blind Treatment					Follow-Up	
	Day 1 Visit	After Day 1, up to Week 24 Visits every 4 weeks (± 5 days)	Week 24 Visit (± 5 days)	After Week 24, up to Week 48 Visits every 8 weeks (± 5 days)	Week 48 Visit (± 5 days)/ Early Termination (ET)		
12-lead electrocardiogram	X		X		X	X	If a participant has a QTcF>480 msec at an on-treatment visit, it should be confirmed by repeat ECG 30-60 minutes after the initial ECG. If the QTcF is confirmed to be >480 msec, the medical monitor should be contacted. See Section 8.5.3.5 and Table 9 in Section 8.5.5
Vital signs	X	X	X	X	X	X	See Section 8.5.3.4
Full physical examination			X		X	X	See Section 8.5.3.3
Abbreviated physical examination	X	X		X			See Section 8.5.3.3
Dual-energy X-ray absorptiometry (DXA)					X		See Section 8.5.3.8. Assessment window \pm 7 days Participants will return for a follow-up DXA assessment 6 months after the Week 52/PTFU Visit (see Table 3). One month is defined as 4 calendar weeks. The ET Visit should include a DXA scan only if the participant has completed at least the Week 16 Visit

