8.4.2 Study Medication Administration

Participants should be instructed to make every effort to administer study medication on the same day each week at approximately the same time of day. Each weekly administration will consist of 2 SC injections.

On Day 1 and at the Week 4, 8, 12, 16, 20, 24, 32, and 40 Visits, study medication will be self-administered by the participant or administered by their designee at the study site as part of the participant's scheduled study visits. At those visits, study medication dosing should be held until all study-related assessments, including participant questionnaires, vital signs, ECG, AE evaluation, physical examinations, and laboratory sample collection (including trough [predose] PK) have been completed.

If a study visit occurs on a day that is not a planned dosing day, the participant should continue to administer the medication on the planned dosing day; all study-related assessments will continue to be performed at the planned study visit (in-clinic administration of study drug would not occur).

Study medication is blinded and is supplied in a pre-filled syringe. Each participant will be dispensed a treatment kit containing 2 smaller boxes (for each weekly administration). Each smaller box will contain 1 prefilled syringe of the medication. Both syringes will be administered in the abdominal area at different locations per training guidelines. Study medication will be assigned by the IRT system.

Guidance and training on administration should be given to the participant (or caregiver, if applicable) prior to the first administration. At a minimum, the first administration should be done by the participant under the supervision of qualified site personnel. Training may be repeated as necessary at any study visit at the discretion of the investigator to maintain treatment compliance. When injections are administered at the site during study visits, site staff may observe the injection to ensure proper technique is being employed. Participants will be required to capture the date, time, and location of each injection on the supplied study medication administration card.

Specific instructions for study medication administration as well as training materials for participants (or caregivers, if applicable) are in the Pharmacy Manual.

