8.5.1 Efficacy Assessments

Every effort must be made to ensure that the same evaluator(s) complete the assessment for each participant. If the evaluator(s) is unable to complete the evaluation, then a qualified individual with overlapping experience may perform the evaluation. Documentation of who performed the evaluation is to be recorded in source documents. Assessments should be performed at approximately the same time of day throughout the duration of the study. Baseline assessments must be performed prior to dosing with study medication. Procedures not specified in the protocol that are part of standard care may be performed if they do not interfere with study procedures; any data arising from such procedures are not to be reported in the eCRF.

All efficacy assessments will be completed prior to study medication administration. Participant questionnaires will be administered electronically, and information gathered electronically (i.e., electronic patient-reported outcome) will serve as the source document where possible.

The following procedures or tools will be used to assess participant's disease activity during the study (see the Schedule of Activities in Section 1):

- Liver biopsy (see Section 8.5.1.1) submitted to the central pathologist at Screening, and at Week 48 or the ET Visit, if applicable
 - Histological assessments of fibrosis stage and NASH activity
 - Assessments of CPA and fat in stained tissue by morphometry
 - Assessments of fibrosis using digital pathology
- Noninvasive measures of fibrosis and/or cirrhosis
 - Noninvasive scores of hepatic fibrosis (see Section 8.5.1.2) (AST-Platelet Ratio Index [APRI], Fibrosis 4 [FIB4] Index, Enhanced Liver Fibrosis [ELF] Score, NAFLD Fibrosis Score) at Day 1, Week 24, and Week 48/ET
 - Liver stiffness as determined by MRE (see Section 8.5.1.3) at Screening, Week 24, and Week 48/ET
 - Liver stiffness as determined by Fibroscan® elastography (see Section 8.5.1.4) at Screening and Week 48/ET
- Hepatic fat fraction as determined by MRI-based proton density fat fraction (PDFF) (see Section 8.5.1.3) at Screening, Week 24, and Week 48/ET
- Physical metabolic assessments (see Section 8.5.1.6) at Screening, Day 1, Week 24, and Week 48/ET
 - Body weight
 - Body mass index (BMI)
 - Waist circumference
- Laboratory Metabolic Assessments (see Section 8.5.1.6) at Screening, Day 1, Week 24, and Week 48/ET
 - Lipids (LDL, HDL, TGs)
 - Fasting plasma glucose
 - Fasting plasma insulin
 - Hemoglobin A1c

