8.5.1.6 Metabolic Assessments

Physical Metabolic Marker Assessments

Body weight, waist circumference, and BMI will be monitored as metabolic assessments.

Weight must be recorded using a calibrated scale, preferably the same scale at each clinic visit. The participant should remove shoes and heavy clothing before standing on scale.

Waist circumference will be measured at the natural waist (smallest waist circumference). If there is no natural waist, the measurement should be made midway between the iliac crest and the bottom of the rib with the measuring tape horizontal all the way around the waist. Measurement should be made at the end of normal inspiration with the participant standing. The waist measurement reported on the eCRF should represent the average of at least 2 measurements. The average measurement should agree within 1 cm. If not, additional measurement(s) should be taken.

BMI is used as an index of obesity and is a method of defining normal body weight and excess body fat. It correlates in a population with percent body fat. BMI is determined by weight (kg) divided by height (m) squared.

Note: All analysis calculations for BMI will be derived internally by the sponsor using height at Screening and weight at the specified time point.

Laboratory Metabolic Assessments

Blood will be drawn according to the Schedule of Events in Section 1 for the following laboratory metabolic marker assessments. Participants should fast for at least 8 hours prior to collection of the blood samples for these assessments.

- Fasting lipids, including LDL, HDL, and TGs. The HDL/LDL ratio will be calculated using the results of these assessments
- Glucose homeostasis markers including fasting plasma glucose, fasting plasma insulin, and hemoglobin A1c

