8.5.3.3 Physical Examinations

Physical examinations may be performed by a Doctor of Medicine (MD) or equivalent, or someone who is authorized to perform the examinations by training and has been delegated this task by the principal investigator.

Full examinations and abbreviated examinations will be performed as specified in the Schedule of Activities (Section 1).

A full examination will include general appearance, skin, head, eyes, ears, nose, throat, neck, thyroid, chest/lungs, heart, abdomen, lymph nodes, extremities, and body weight.

Abbreviated examinations will include an abdominal exam and symptom-focused assessments. An abbreviated examination may note any changes in the participant's condition (body systems) since the last assessment and does not preclude examination of any of the other body systems as clinically indicated. Every effort should be made to ensure the same evaluator will complete the examination for each participant at all visits throughout the study. Documentation of who performed the examination is to be recorded in source notes.

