8.5.3.4 Vital Signs

Schedules for vital sign collection are provided in Section 1. Vital signs will include heart rate, respiratory rate, sitting SBP and DBP (to be taken after at least 5 minutes sitting at rest), and oral temperature.

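### The >10% weight-loss trigger is backed by a scheduled weight at only one of the eight dosing visits after Day 1 (Week 24)

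*Protocol*

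**What the plan says.** **The trigger.** Protocol 8.3.9.1 includes, among the reasons for discontinuing study medication: "If a participant loses more than 10% of their total body weight, the investigator should contact the medical monitor". Investigator and monitor then decide together whether the participant stays on drug. No reference weight is named. Section 8.5.3.1 uses a similar threshold, a change of at least 10% from Baseline not explained by lifestyle alone, for calling a weight change an adverse event.

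**The weights.** The Table 2 row "Weight for body mass index (BMI) calculation" is marked at Day 1, Week 24, Week 48/ET and follow-up. Both interim-visit columns are blank. Section 8.5.1 agrees for the treatment period: "Physical metabolic assessments (see Section 8.5.1.6) at Screening, Day 1, Week 24, and Week 48/ET".

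**Other procedures that might supply a weight.**
- Section 8.5.3.3 ends its list for the full examination with "lymph nodes, extremities, and body weight", but Table 2 places that examination only at Week 24, Week 48/ET and follow-up.
- The interim visits use the shorter form: "Abbreviated examinations will include an abdominal exam and symptom-focused assessments".
- Section 8.5.3.4, at every visit: "Vital signs will include heart rate, respiratory rate, sitting SBP and DBP", plus temperature. Weight is not listed.
- Section 8.5.1.6 says "Weight must be recorded using a calibrated scale, preferably the same scale at each clinic visit". This concerns which scale to use; it does not add a weighing to Table 2.

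**The dosing visits.** Section 8.4.2 has in-clinic dosing "On Day 1 and at the Week 4, 8, 12, 16, 20, 24, 32, and 40 Visits", after that visit's assessments are complete.

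**The concern.** A rule that depends on a measured change needs the measurement while the decision can still be taken. Between Day 1 and Week 24, and again from Week 24 to the last dose, no scheduled weight could reveal a loss above 10%. Detection at seven of the eight visits rests on an unscheduled weighing, the general safety review described in 6.3.3, or the participant's own report.

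Other laboratory-based triggers in the same list are better served. The eGFR and liver-test rules are backed by blood chemistry at every visit through Week 52 (Table 8).

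The stake is continued dosing during a loss that the protocol wants reviewed. Section 6.1.1 attributes the animal bone findings, except at the highest monkey dose, to drug-mediated weight effects and slower growth. The first-in-human study saw lower weight than on placebo at doses up to 30 mg daily for up to 14 days (6.1.2). Treatment here lasts 48 weeks, against 12 and 16 weeks in the earlier Phase 2 studies. On-treatment DXA does not fill the gap, because for completers it also comes at Week 48.

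A secondary point: SAP 8.1 keeps unscheduled measurements out of descriptive statistics, so an off-schedule weight would not reach the group summaries unless used as baseline.

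**Working it through.** The plan states no figure to reproduce. The check is a count of visits and doses.

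**Inputs.** Visits every 4 weeks to Week 24 and every 8 weeks to Week 48, with 48 weekly doses (Protocol 8.1); dosing visits (8.4.2); weight and examination rows of Table 2; Day 169 as the day of the Week 25 dose (Table 9).

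**Visit count.** The visit interval gives Weeks 4, 8, 12, 16, 20, 24, 32, 40 and 48. Without Week 48, this is the list in 8.4.2: 8 visits. Those with a weight from either the weight row or the full examination: Week 24 only. So 1 of 8 has a scheduled weight and 7 do not.

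**Dose timing.** Dose k falls at Week k − 1. Dose 25 is at Week 24 (Day 24 × 7 + 1 = 169, matching Table 9). Dose 48 is at Week 47 (Day 47 × 7 + 1 = 330), before the Week 48 weight.

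**Doses given before the next scheduled weight:**

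| Time of crossing 10% | Current schedule | Weight at every dosing visit |
|---|---|---|
| By the Week 4 visit | doses 5–24 = 20 | 0 if found at Week 4; doses 5–8 = 4 if just after that weighing |
| Just after the Week 24 weighing | doses 25–48 = 24 | doses 25–32 = 8 |

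The longest gap between scheduled weights during treatment is 24 weeks now. It would be 4 weeks up to Week 24 and 8 weeks after it.

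**Average wait.** The documents give no rate or timing of crossings, so the timing is an assumption. The share column is the fraction of crossing times for which a scheduled weight still falls before the last dose.

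| Assumed timing (uniform within period) | Mean wait now | Mean wait with fix | Share now | Share with fix |
|---|---|---|---|---|
| Weeks 0–48 | 24/2 = 12 wk | 0.5 × (4/2) + 0.5 × (8/2) = 3 wk | 24/48 = 50% | 40/48 = 83% |
| Weeks 0–24 only | 24/2 = 12 wk | 4/2 = 2 wk | 100% | 100% |
| Weeks 24–48 only | 24/2 = 12 wk | 8/2 = 4 wk | 0/24 = 0% | (40 − 24)/24 = 67% |

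If crossings come late, which is plausible for a loss that builds up, the current schedule does worse: no scheduled weight after Week 24 precedes the last dose.

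**The case against.** The count is not in dispute; its importance is.

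- **The trigger is discretionary.** It prompts a conversation and sets no stopping limit. A loss above 10% is not subtle (more than 9 kg at an illustrative 90 kg). Section 6.3.3 requires a safety evaluation before dosing, adverse events are sought by open questioning, and the abbreviated examination allows further examination when indicated. This stands. The dose counts and waits above assume that these routes detect nothing, so they describe scheduled detection only.
- **Crossings may be rare.** The 12-week diabetes study saw no meaningful weight change (6.1.2). Exposure at 40 mg weekly is expected to be below that of 10 mg daily (6.2.2). Section 8.3.2 excludes a change of 10% or more in the 26 weeks before Screening or during it. This limits how many participants could benefit, and the number may be close to zero.
- **Human bone data are reassuring.** Section 6.3.2.4 reports no effect on bone density over 12 or 16 weeks. Low T-scores are excluded from age 40, and DXA, adverse events of special interest and a DMC add oversight. This lowers the likely harm but supplies no weight during treatment.
- **Not every trigger in the list is measured at each visit.** Fracture and osteoporosis rely on reports or late DXA. True, but weight is far cheaper to measure than bone density.
- **The reference weight is fairly clear.** Section 8.5.3.1 and SAP 8.1 both point to Baseline. Accepted; naming it is tidying.
- **Timing of the amendment.** Version 4.0 is dated 30 January 2020, 252 days (36 weeks) before the 8 October 2020 cut-off. If the cut-off covers every participant's Week 52, the last was at about Week 52 − 36 = 16 by then. The full-schedule gain was mostly out of reach in this version.

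**Conclusion.** The concern holds as a gap in scheduled detection. One of the eight post-Day-1 dosing visits has a scheduled weight; the gaps are 24 weeks before and after it, and up to 24 doses can be given before the next scheduled weight. The visit and dose counts rest on the documents alone. The average waits rest on assumed timing of crossings, but the current wait is 12 weeks under all three assumptions shown, against 2 to 4 weeks with the fix.

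This does not make the rule inoperative, and it does not show that anyone is harmed. How many participants would cross 10% unnoticed cannot be estimated from the documents. The case for change is that a stated safety rule can be made checkable at every dosing visit for very little. It is a worthwhile improvement, not a critical defect.

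**What to change.** - In Table 2 and the timing line of 8.5.1, add body weight at the existing Week 4, 8, 12, 16, 20, 32 and 40 visits, before dosing.
- In 8.3.9.1, name Baseline (Day 1) weight as the reference, in line with 8.5.3.1.
- Leave the 10% threshold and the joint decision as they are. The Week 24 and Week 48 timing of the exploratory weight endpoints need not change.

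The cost is protocol and eCRF wording, one extra eCRF field, and about a minute on the scale at seven existing visits. No new visit or staff is needed. Expect some additional contacts with the medical monitor, including for intended loss, since 8.3.6 counsels overweight participants to reduce weight. If introduced at version 4.0, after enrollment closed, the change reaches only the visits still to come.
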